### **Aim 2- Training Intervention:**

Study procedures are outlined in the figure below. After screening, eligible participants complete the online informed consent form and the locator form. The locator form records the participant's home and work telephone, address, email, and the contact information of others who may be able to assist research staff to reach the participant, if needed. This information will be used to prompt participants to join the scheduled interview. Only study staff will have access to this information. Participants will be contacted primarily through email to ask them to complete surveys or to schedule online mock counseling sessions, but we will secondarily use text, calls, letters, and social media direct messaging as reminders. Participants will complete the self-administered baseline instruments using Alchemer software and be scheduled to complete an online mock counseling session.

After both the baseline survey and mock counseling session have been completed, participants will be randomized into one of three groups using a blocked randomization procedure. The block randomization procedure is used to control for level of education (high school/GED, bachelors, masters, PhD) and training and experience in Cognitive Behavior Therapy (CBT) and Applied Behavior Analysis (ABA), as CRAFT is a CBT based on ABA principles.

We will use an additive components design consisting of: 1) digital tutorial only (T), 2) digital tutorial plus digital training materials (TM), and 3) digital tutorial and digital training materials plus feedback and coaching (TMC). This design will allow us to assess whether the digital training materials improve counselor outcomes relative to the tutorial only, but will not allow us to assess their contribution, if any, to the full training product (TMC).

Follow-up assessments will be conducted after all three groups have completed the tutorial (at 2 weeks) and again at 12-weeks post baseline. All aspects of the study will be conducted completely virtually.

Table 1. Treatment Conditions

TREATMENT CONDITION	Pre-tutorial Assessment	Tutorial	Post-Tutorial Assessment	Experimental Manipulation	12-week Follow-up
	Week 0	Week 1-2	Week 2		Week 12
Digital Tutorial (T)	A	Digital Tutorial	B	Weekly emails encouraging review of specific modules and continued use of the online tutorial	C

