### **Aim 2- Training Intervention:**

#### ***Data collected directly from participants:***

Surveys for baseline, post tutorial (i.e., 2-weeks post baseline), and 12-weeks post baseline assessments will be self-administered using Alchemer software since participants may be located anywhere across the country. The baseline survey consists of socio-demographic questions, such as gender, age, race/ethnicity; other standardized socio-demographic measures adapted from the GPRA instrument; a CRAFT Knowledge Test; and a Training Expectations Form.

Each assessment point also will include an audiotaped mock client session conducted via web conferencing with a standardized patient portrayed by a professional actor. Using a standardized patient will provide a consistent context for measuring counselors' CRAFT skill level at each time-point. The mock session will present the counselor with an opportunity to roleplay CRAFT procedure: teaching the CSO to invite the IP to enter treatment (the same procedure is required for the follow-up assessments). We chose to assess this procedure because a component analysis study showed it positively impacted treatment entry rates and it requires CRAFT skill accumulation (i.e., it incorporates and builds upon skills trained in communication and positive reinforcement). Audio tapes will be coded using the CRAFT Therapist Coding Manual used by [name] to certify counselors.

At the post-tutorial and 12-week follow-up assessments additional surveys will be added regarding satisfaction with the training program, perceptions of usefulness and usability, implementation potential, and program value. Finally, at the 12-week follow-up only, participants will be asked to report the number of CSOs they have worked with over the past 10 weeks, how many of them they implemented CRAFT with, and how many of those CSOs had a loved one who entered new treatment. The measures, their purposes, related hypotheses, and assessment points are provided in the **Measures Table** below.

Table 3. Measures

Purpose	Hypothesis	Measure	Assessment points 
Counselor Knowledge and Skill	i. TMC>TM>T	CRAFT Therapist coding Manual***	Pre-Tutorial, Post-Tutorial, 12 weeks
	ii TMC>TM>T	CRAFT Knowledge Test**	Pre-Tutorial, Post-Tutorial, 12 weeks
Acceptability and Feasibility	iii	Training Expectations Form x	Pre-Tutorial
	iii	Training Satisfaction Survey x	Post-Tutorial, 12 weeks

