Cover Page: Statistical Analysis Plan
We The Village Counselor Training Study
NCT05875142
Document Date: 09.26.23

Statistical Analysis Plan

Our statistical analysis focuses on a primary endpoint as well as a number of secondary endpoints of interest. The data derive from questionnaires collected from participants in the study. The final enrollment involved three groups: T – Digital Tutorial Overview, TM – Digital Tutorial Plus Training Materials, and TMC – Digital Tutorial Plus Training Materials Plus Feedback and Coaching, with 15, 16, and 16 subjects enrolled, respectively.

1. **T – Digital Tutorial Overview:** Participants assigned to T were given access to a digital tutorial consisting of a curriculum dashboard for review of 10 modules, including videos, PDFs, text and quizzes, which are to be self-administered over two weeks. Modules remain available during the 10-week post tutorial period. Participants receive weekly contact encouraging engagement in all of the materials available to them.
2. **TM – Digital Tutorial Plus Training Materials:** Participants receive the digital tutorial (T) as described above plus access to 10 modules of digital training materials released weekly over the 10-week post tutorial period for self-study. Participants receive weekly contact encouraging engagement in all of the materials available to them.
3. **TMC – Digital Tutorial Plus Training Materials Plus Feedback and Coaching:** Participants receive the digital tutorial (T) plus the digital Training materials as described in the two arms above plus they submit audio recordings of sessions with clients and receive feedback on their application of CRAFT and coaching on how to improve. Participants receive weekly contact encouraging engagement in all of the materials available to them.

Our comparisons are all treatment/control comparisons of T with TM, and T with TMC.

1. Primary Hypothesis
 - 1.1. At 12 weeks (after study start), participants assigned to the TMC condition will demonstrate the highest CRAFT procedure fidelity (measured in audiotaped sessions with a standardized patient) followed by TM and then T.

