Rationale: Direct observation measuring content of CRAFT delivered in treatment sessions is our primary outcome as this provides the best assessment of counselor adherence and skill and is consistent with previous studies.^{7,10,41} Our hypothesis that TMC will produce greater use of CRAFT than T (or TM) is based on the results from previous trials comparing a workshop only to workshops plus feedback and coaching.^{7,10,41}
2. Secondary Hypotheses
 - 2.1. Participants assigned to the TMC condition will demonstrate the highest CRAFT knowledge followed by TM and then T, in their 12-week knowledge test.
Rationale: Results from previous controlled trials have shown no differences in counselor knowledge pre- to post-workshop, but increases have been seen when fact sheets and supervision are added after the workshop.^{39,57-58}
 - 2.2. Participants in all conditions will perceive increased implementation potential over time (pre-tutorial, post-tutorial, 12 week follow up), but at 12 weeks implementation potential will be lower for TMC compared to TM and T.
Rationale: In a CBT (Cognitive Behavioral Therapy) web-based training study implementation potential of three training programs increased over time, but a condition involving expert supervision was seen as more difficult to implement.³⁹

2.3. Participants assigned to the TMC condition will report that more IPs have entered treatment compared to TM and T at 12-weeks (after study start) follow-up surveys. *Rationale:* This hypothesis is based on the results from previous trials examining counselor fidelity^{7,10,41} and studies showing that CBT fidelity enhances treatment outcome.⁵⁹⁻⁶⁰ *We consider this hypothesis exploratory because the 6 month timeline will not be sufficient to adequately test for differences in treatment entry, as there would not be much time after all counselors completed training for them to complete CRAFT with CSOs.*

Data Analysis

Primary and secondary hypotheses were investigated by computing the improvement from baseline to 12-week timepoints. One-sided independent samples T-tests were used for pairwise comparisons of the three conditions. One-sided tests are appropriate for our hypothesized conditions: the alternative hypotheses for which we seek evidence is TMC is better than T, TM is better than T, and TMC is better than TM.

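### Randomisation is blocked on education and CBT/ABA background, but the t-tests omit these factors; if they predict fidelity change, the tests are conservative and power is lost

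*Protocol*

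**What the plan says.** Protocol section 4.1, Aim 2, states that "participants will be randomized into one of three groups using a blocked randomization procedure". It gives the purpose as follows: "The block randomization procedure is used to control for level of education (high school/GED, bachelors, masters, PhD) and training and experience" in CBT and ABA. The reason offered is "as CRAFT is a CBT based on ABA principles". The section gives no block size, no categories for CBT/ABA background, and no figure for how strongly either factor relates to fidelity.

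The SAP's Data Analysis section defines the analysed quantity: "Primary and secondary hypotheses were investigated by computing the improvement from baseline to 12-week timepoints". The test is: "One-sided independent samples T-tests were used for pairwise comparisons of the three conditions". No covariate, stratum term or adjusted sensitivity analysis is named. Enrolment in T, TM and TMC is given at the start of the SAP: "with 15, 16, and 16 subjects enrolled, respectively". Alpha, target effect, SD and power appear in neither document.

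**The concern.** The design treats education and CBT/ABA background as factors worth controlling, and the analysis then drops them. Blocking makes the arms more alike on these factors, so the difference in means varies less from one randomisation to the next. The two-sample t-test does not know this. Its standard error is built from the total within-arm variance, including the part due to the factors, as if allocation had been unrestricted. If the factors matter for the outcome, the standard error overstates the true variability and the test rejects too rarely. Blocking in small strata is also only approximate, so some chance imbalance stays in an unadjusted estimate. With 15 or 16 counselors per arm, any precision the design has bought is worth keeping.

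**Working it through.** **No plan figure to reproduce.** The documents state no standard error, alpha, effect size or power.

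**Inputs from the documents:** T 15 and TMC 16, out of 47 enrolled; blocked allocation to three arms; four education levels; t-test on change from baseline, one-sided.

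**Inputs assumed:** alpha 0.05 (0.025 as alternative); effect d = 0.8 in SDs of the change score (0.5 and 1.0 as alternatives); blocks of three; no dropout; R² = share of change-score variance explained by the factors, 0 to 0.40; either 8 cells (4 education × 2 for CBT/ABA combined) or 16 cells (4 × 2 × 2, CBT and ABA separate).

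**Step 1: closed form.** The standard error in SD units is √(1/15 + 1/16) = 0.359. The planned test has 15 + 16 - 2 = 29 df and noncentrality 0.8/0.359 = 2.23, giving power 70.1%. With adjustment the residual SD is multiplied by √(1 - R²), and 4 df go to the factors (3 education, 1 CBT/ABA). For example, at R² = 0.20 the noncentrality is 2.23/√0.80 = 2.49 on 25 df, giving power 78.1%.

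| alpha, d | t-test | adjusted, R² = 0 | 0.10 | 0.20 | 0.30 |
|---|---|---|---|---|---|
| 0.05, 0.5 | 38.7% | 38.5% | 41.4% | 44.8% | 48.9% |
| 0.05, 0.8 | 70.1% | 69.9% | 73.8% | 78.1% | 82.7% |
| 0.05, 1.0 | 85.8% | 85.6% | 88.6% | 91.6% | 94.4% |
| 0.025, 0.8 | 57.6% | 57.1% | 61.6% | 66.7% | 72.5% |

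This slightly flatters adjustment. It holds unadjusted power fixed, although blocking alone raises it a little when the factors matter, and it assumes the factors are perfectly balanced across arms.

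**Step 2: simulation of the blocked design.** 6,000 trials per setting, N = 47, TMC v T, one-sided 5%, d = 0.8, SD of change = 1. The adjusted model has main effects only. The 16-cell runs assume a mix of education 10/25/55/10%, CBT 60% and ABA 25%.

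| Cells | R² | t-test SE v true SD of estimate | t-test type I error | Power, t-test → adjusted |
|---|---|---|---|---|
| 8 | 0 | 0.358 v 0.355 | 5.3% | 70.7% → 69.1% |
| 8 | 0.10 | 0.359 v 0.344 | 4.6% | 71.2% → 73.1% |
| 8 | 0.25 | 0.360 v 0.320 | 3.0% | 72.4% → 79.9% |
| 8 | 0.40 | 0.361 v 0.295 | 2.3% | 73.1% → 86.8% |
| 16 | 0 | not tabulated | not tabulated | 70% → 69% |
| 16 | 0.10 | not tabulated | not tabulated | 71% → 73% |
| 16 | 0.20 | 0.358 v 0.332 | 3.8% | 71% → 77% |
| 16 | 0.30 | SE about 13% too wide | 3.5% | 72% → 82% |

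Monte Carlo 95% error is about 0.6 points for type I error and 1.2 points for power. One repeat of the 16-cell run at R² = 0.20 gave a type I error of 4.4%. In the 8-cell runs the adjusted model held type I error at 4.9 to 5.4%.

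**Step 3: is blocking the cause?** With simple randomisation and R² = 0.25, the t-test standard error is right (0.358 v 0.356, type I error 5.1%). With blocking it is 0.360 v 0.320, a ratio of 1.125, or about 12% too wide. So the excess width comes from blocking on the factors and then ignoring them.

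**The case against.** The strongest objection is that nothing in the documents shows the factors predict the analysed outcome. The protocol's reason is qualitative, and the SAP analyses change scores. Education and prior CBT/ABA training may act mainly through baseline skill, which the change score already subtracts. At R² = 0 adjustment costs a point or two; at 0.10 the gain is small. This stands, and it makes the loss conditional.

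The error is also in the safe direction, in a Phase I pilot whose stated aim includes feasibility and acceptability. That stands too: this is a matter of efficiency and of matching the analysis to the design.

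A reader might infer more than the documents support:

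- **That reported standard errors or confidence intervals are wrong.** Neither document states any; the SAP names only t-tests.
- **That there are at least 16 cells, each holding less than one block.** CBT and ABA can be read as one factor, giving 8 cells and 47/8 = 5.9 counselors per cell, against 47/16 = 2.9 if separate. No block size is stated. The power pattern is similar either way.
- **That CBT/ABA status is not collected, or that the education levels are faulty.** Section 4.2 gives an illustrative list ("The baseline survey consists of socio-demographic questions, such as gender, age, race/ethnicity") and then refers to further measures. At most, detail is missing.

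Lastly, the SAP is in the past tense. If the analysis has been done, replacing the primary test would be a post-hoc change. This is a fair limit on the remedy.

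**Conclusion.** The mismatch is plain: the randomisation factors are absent from the planned analysis. The consequence is conditional. If education and CBT/ABA background predict change in fidelity, the t-tests would be conservative and would lose power; they would not produce excess false positives.

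Across the 8-cell and 16-cell readings, at one-sided 5%, d = 0.8, 15 v 16 and no dropout, adjustment changes power by about -1 to -2 points at R² = 0, +1 to +3 at 0.10, +6 at 0.20 and +9 to +10 at 0.30. R², alpha, effect size and block size are all assumptions. The SAP gives numbers enrolled, not numbers completing, so real power may be lower under either analysis. The flat statement that power is lost goes beyond the documents. The change is still worth making, because the possible gain is larger than the small loss if the factors prove irrelevant.

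**What to change.** Analyse fidelity improvement with one linear model over all three arms, containing arm plus the randomisation factors with the values used for allocation. Use main effects only, merge sparse education levels, and read the three pairwise contrasts from this model. State alpha, the block size and the CBT/ABA categories, so that the factors in the model can be seen to match those in the allocation.

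The cost is about 3 to 5 residual degrees of freedom. A three-arm model with arm alone has 47 - 3 = 44; adding the factors leaves 39 to 41, still more than the 29 of the T v TMC t-test. If the factors are unrelated to the outcome, the loss is about 1 to 2 points of power. No new participants, visits or measurements are needed, provided the allocation values were kept.

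If the t-tests have already been run, keep them as planned and report the adjusted model beside them, labelled as added later.

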### **Treatment Conditions:**

**Digital Tutorial (T)** - All participants will continue to have access to tutorial materials throughout the study. Participants assigned to the T condition receive ONLY the tutorial. Afterwards they will be encouraged via weekly emails that are a component of the training program to continue using the resources in the online tutorial to revisit the CRAFT lessons on their own during the 10-week period between post-tutorial follow-up and the final follow-up assessment.

**Digital Tutorial, with training materials (TM)** - Participants assigned to the TM condition will complete the tutorial and then receive access to the additional training materials. They will not receive any feedback or video-calls for coaching. They will be encouraged via weekly emails to continue to learn CRAFT on their own during the 10-week post-tutorial period by using the new resources in the online tutorial and the digital training materials.

**Digital Tutorial, with training materials plus feedback and coaching (TMC)** - Systematic feedback and coaching during the 10-week post-tutorial to final assessment period (12 weeks post-baseline) will be provided to only to the 15 participants assigned to the TMC condition. Participants will be required to submit audio taped sessions with clients. They will be provided with consent-to-audiotape forms that they will need to have the client complete prior to

audiotaping sessions with that client. If their place of work also has required client consent-to-audiotape forms, they will need to have the client sign both forms, or receive permission from their place of employment to use the form we provide instead. We will provide a brief training to prepare the counselors to attain informed consent to audiotape from clients. The training will be delivered via a zoom session with supporting written materials. The training will emphasize that the informed consent process is based on respect for the individual, and, in particular, the individual's autonomy or capacity and right to make choices. They will be taught to convey accurate and relevant information about their reasons for requesting permission to audio record, namely, to meet the requirements of a study that they are participating in, letting the client know that the purpose of the study is to examine different counselor training methods and that it is the counselor's behavior that is the target of these recordings. Counselors will be taught to inform clients of the known risks (the potential of breach of confidentiality) and that all audiotaping and management of audio files will be done using HIPAA compliant methods to reduce risks. Counselors will be trained to inform clients that they may experience no direct benefit from agreeing to audiotaping. We will emphasize that clients must be informed that they may refuse taping without any penalty; they must not be treated any differently by the counselor or the clinic. They will be instructed to allow clients to ask questions and have them answered so that they can make an informed decision about whether to participate. The training will also emphasize that consent is always voluntary, and participants may withdraw consent at any point in time. They will be asked to store the forms in a secure place where they normally keep confidential patient materials. In order to protect client confidentiality, we will not collect or keep copies of these forms, as they would provide additional client identifying information that is not required for the study.

In addition to providing training in the informed consent procedure, counselors will be trained in procedures to protect the confidentiality of the audiotaped sessions. They will be trained to ask clients to avoid using names and instead to refer to the IP in terms of their relationship (e.g., my son, my partner). Sessions will be taped using one of three procedures. First, if the counselor has access to a HIPAA compliant electronic patient health platform that supports audio recording sessions (e.g., SimplePractice) and securely transmitting them (e.g., via encryption), we will accept use of their established system. Second, if their practice does not provide this type of software, we will have counselors download free software (i.e., Pocket Dictate Mobile Dictation Recorder) that allows them to audiotape the session on their telephone and send the encrypted recording to us. Counselors will be instructed to delete the recording immediately after receiving confirmation of receipt. As an additional precaution, they will be shown how to adjust the application settings so that the audio recordings are automatically deleted after 24 hours and instructed to password protect their phone so that only they can access it. Third, if the counselor does not have access to either a HIPAA compliant electronic patient health platform or a smartphone, we will provide them with a digital audio recorder that allows them to securely upload files directly to a HIPAA-compliant server. They will be instructed to delete the audio recording from the device immediately after uploading to this system.

Participants will digitally receive written feedback and live video-call coaching on their tapes (up to 12 allowed). They will be encouraged to re-submit their audio taped sessions until they meet the criteria needed for certification in the CRAFT procedure or until the phase is over (whichever occurs first).

[figure not shown]
Participants will receive individual written Personal Performance Feedback on all audio taped sessions that they submit. This feedback is generated by two CRAFT certified trainers (i.e., CRAFT Trainer or CRAFT Coder) who access the digitally audio taped sessions via a secure server. The trainer listens to the audiotape and records a session content checklist that indicates key procedures for each module. For each key component, the trainer indicates whether it was addressed in the session, rates the quality of implementation for that component (1=poor to 5=excellent), and writes comments praising specific behaviors or making suggestions for further improvement. This feedback is password protected and emailed to the counselor. TMC participants will participate in weekly 30-min video-call Coaching Sessions. In addition, the audio taped client sessions will be accessed by research team members charged with developing software that would automatically complete the coding currently done by the CRAFT trainers.

Table 2. Study Activities By Program

STUDY ACTIVITIES BY PROGRAM		
Tutorial	Tutorial + Materials	Tutorial, Materials, & Coaching
• Digital Tutorial providing CRAFT principles overview.	• Digital Tutorial providing CRAFT principles overview.	• Digital Tutorial providing CRAFT principles overview.

• Weekly emails encouraging continued use of the online tutorial to revisit CRAFT lessons.	• Additional training materials providing in-depth instruction on CRAFT protocol nuances and techniques.	• Additional training materials providing in-depth instruction on CRAFT protocol nuances and techniques.
	• Weekly emails encouraging continued use of the online tutorial and materials to revisit CRAFT lessons.	• Systematic feedback and coaching on CRAFT protocols and techniques 10-week period.
		• Program weekly emails encouraging continued use of the online tutorial and materials to revisit CRAFT lessons.

Figure 3. Recruitment and Enrollment Flowchart

**4.2 Briefly describe the sources or measures that will be used to collect data about participants. As applicable, include information on: instruments or surveys that will be administered, tests that will be performed, and the time points when each data will be accessed or obtained.**

